21.2.4 Authorship of primary and ancillary publications

First authorship of the primary publication will be offered to the Coordinating Investigator. Investigators with the highest score will be considered for remaining positions.

The authorship of ancillary publications will be based on contribution to conception and design of the publication, analysis and interpretation of data, the score, and authorship on previous publications.

21.2.5 Timelines and compliance

The publication plan gives a detailed overview of timelines for preparation and submission of publications. If the first author will not provide a manuscript within appropriate time after a reminder, a co-author may be invited to become first author.

The Publication Team will ensure that authorship guidelines are met and authorship is attributed appropriately. The Publication Team will also track timeline adherence.

21.2.6 Reimbursement

No honoraria will be paid for authorship of publications.

21.3 Contributorship and acknowledgement

Individuals, including BIOTRONIK employees, who have substantially contributed to a publication, but who do not meet the authorship criteria, should be listed in the

acknowledgement section. Any support provided by a professional medical writer must also be disclosed in the acknowledgement section.

21.4 Ancillary publications

Ancillary publications are publications in addition to the primary publication. All study stakeholders (e.g. participating investigators, BIOTRONIK employees) may submit publication ideas through the Publication Team.

The Publication Team must approve suggestions for ancillary publications and will ensure that these publications are not in conflict with previously submitted suggestions. Requests for ancillary publications will be evaluated for scientific validity and the ability of BIOTRONIK to provide resources.

23 APPENDICES

Cardiac Perforation – Penetration of the lead tip through the myocardium (including microperforation), either clinically suspected or confirmed by chest x-ray, fluoroscopy, echocardiogram, intracardiac electrogram and/or visually.

Exit block - stimulation threshold exceeds the pacemakers` programmed output

Hematoma – A localized collection of extravasated blood, usually clotted, in an organ, space, or tissue.

Incorrect Lead/Header Connection – Lead connector pin connected to wrong header port, such as swapping leads or reversing connector pins, that is not identified and corrected prior to the end of the implant/revision procedure.

Infection – An invasion and multiplication of microorganisms in body tissues causing local cellular injury and requiring pharmaceutical and/or surgical treatment.

Lead Dislodgment – Radiographic, electrical or electrocardiographic evidence of electrode displacement from the original implant site or electrode displacement that adversely affects pacing, and/or lead performance.

Lead Explant – Surgical removal of a lead either by simple traction (such as occurs during the acute implant stage) or using manipulation and tools (as can be required for chronically implanted leads).

Lead Impedance Out of Range – Pacing impedance is considered abnormal if a measurement is ≤ 200 Ohms (low impedance) or ≥ 2000 Ohms (high impedance).

Lead Undersensing – Intermittent failure to sense any intrinsic events that occur outside the programmed refractory periods at programmed sensitivity settings.

Loose Set Screw – Header set screw not properly tightened prior to end of implant/revision procedure.

Loss of Sensing – Complete failure to sense any intrinsic events that occur outside the programmed refractory periods at programmed sensitivity settings.

New York Heart Association (NYHA) Functional Classification – A recognized system of classifying the extent of heart failure.

Table 10: Definition of NYHA classes

NYHA Class	Symptoms
I	Ordinary physical activity does not cause undue fatigue, palpitation, dyspnea, or anginal pain
II	Ordinary physical activity results in fatigue, palpitation, dyspnea, or anginal pain
III	Less than ordinary physical activity causes fatigue, palpitation, dyspnea, or anginal pain
IV	Symptoms of cardiac insufficiency or of the anginal syndrome may be

	present even at rest. If any physical activity is undertaken, discomfort is increased.
--	--

No Capture (Loss of Capture) – Complete failure to achieve cardiac stimulation at programmed output delivered outside of the cardiac refractory period.

No Output – Pacing pulses are provided by the device but not transferred by the lead

Pneumothorax – Air or fluid in the pleural space surrounding the lung leading to collapse or partial collapse of the lung.

Pocket Pain – Pain in the area of the pulse generator implant that lasts longer than typically associated with the procedure and requires pharmaceutical and/or surgical treatment.

Premature Battery Depletion – Reaching elective replacement indicator (ERI) before the predicted date.

Pulmonary Embolism – Blockage of the main artery of the lung or one of its branches by a substance that has travelled from elsewhere in the body through the bloodstream.

Pulse Generator Failure – Confirmed or suspected pulse generator issue that is due to a mechanical failure or electrical malfunction, such as inability to communicate with pulse generator, electrical circuit failure, or inability to deliver therapy, that is not attributable to another component of the system or caused by an external source.

Skin Erosion – Deterioration of tissue over an implanted device or the movement of a lead toward or through the skin.

Tamponade – Compression of the heart caused by blood accumulation in the space between the myocardium and the pericardium.

Thrombosis – The development of a blood clot in a vein or artery that leads to the obstruction of blood flow.

Total Procedure Time – Time (hours and minutes) required to complete implant procedure from initial incision/puncture to last suture.

Twiddler's Syndrome – A condition where the pulse generator leads are dislodged by the subject unwittingly rotating or otherwise moving the subcutaneous pulse generator.

Venous Occlusion – Blockage of a vein causing a reduction of blood supply and associated symptoms

22.6.	Hypotheses & Statistical Tests	64
23.	Primary Endpoint 2: SADE-free Rate Plexa	65
23.1.	Analysis set	65
23.2.	Variables	65

23.3.	Treatment of Missing and Spurious Data	67
23.4.	Exclusion of Particular Information	67
23.5.	Descriptive Analyses	67
23.6.	Hypotheses & Statistical Tests	67
23.7.	Alternative analysis (as suggested by the study objective)	67
24.	Secondary EP: Rate appropriate RV sensing Plexa	68
24.1.	Analysis set	68
24.2.	Variables	68
24.3.	Treatment of Missing and Spurious Data	68
24.4.	Exclusion of Particular Information	68
24.5.	Descriptive Analyses	68
24.6.	Hypotheses & Statistical Tests	68
25.	Secondary EP: Rate appropriate RV pacing Plexa	69
25.1.	Analysis set	69
25.2.	Variables	69
25.3.	Treatment of Missing and Spurious Data	69
25.4.	Exclusion of Particular Information	69
25.5.	Descriptive Analyses	69
25.6.	Hypotheses & Statistical Tests	69
	Abbreviations	70

1. Introduction

The aim of this document is to provide detailed instructions on all mandatory descriptive and inferential statistical analyses for the Clinical Investigation Report.

The text contains verbatim excerpts from the CIP. Such excerpts are italicized with grey background; e.g.

This study is designed as post market clinical follow-up study to identify and evaluate residual risks associated with the use of the Ilivia ICD family and the Plexa ICD lead that are unveiled...

The main aspects and the design of the clinical investigation are presented in chapters 2 to 4. General statistical procedures are summarized in chapter 5. Those methods are used in case there is no other instruction within this document.

Definitions of the specific dates, e.g. effective randomization and termination are presented in chapter 0.

Specific analysis sets are defined in chapter 7.

General data for the complete study are handled in chapter 8. Data related to the Ilivia group and for the Plexa group are handled separately in the subsequent chapters.

Thereby the following statistical considerations are specified:

- Definition of the analysis set for the following analyzes, e.g. excluding patients without any measured or imputed data for this endpoint.
- Definition of the endpoint(s) to be analyzed including references to the source data, e.g. CRF sheet and item.
- Treatment of missing and spurious data for evaluation of the above endpoint(s).
- Exclusion of particular information from the evaluation of the above endpoint(s) in addition to the exclusion of patients from the analysis set.
- Descriptive analyses including tables and figures
- Statistical alternative hypothesis/hypotheses (HA) to analyze the above endpoint(s).
- Statistical tests intended to analyze the above hypothesis/hypotheses.

All variables are defined in tables using the following columns:

Data file	Name of a data file exported from the CDMS with one data row per unique identifier (e.g. patient specific "patient_display_ID_full"). Additionally, a new data file ("data_SAR") is generated by merging all relevant data from the original CDMS data files and generating derived variables (e.g. BMI from weight and height or date of first AE episode)				
Descriptive	Information whether data has to be presented with descriptive methods as defined in the following sub-chapter ("Yes") or data needed for generating of derived variables only ("No")				
Variable name	Original name of a variable in the CDMS data file or name of a derived variables (indicated with a suffix "_SAR");				
Variable label	Variable label which might be shortened ("...") if remaining clear; note that original labels from the CDMS data will be used for generating the Statistical Analysis Report unless a new label is defined in this document ("NEW")				
Variable level	Nominal, ordinal, scale (metric, continuous), or date				
Nominal values	Values might be shortened ("...") if remaining clear; note that original values from CDMS data will be used for generating the Statistical Analysis Report unless new nominal values are defined in this document ("NEW"); for numeric data this information is not applicable (n.a.)				

Data file, unique identifier	Descriptive	Variable name	Variable label	Variable level	Nominal values
patient_display_id_full					

2. Objectives

CIP chapter 7.1 Objectives

This study is designed as post market clinical follow-up study to identify and evaluate residual risks associated with the use of the Ilivia ICD family and the Plexa ICD lead that are unveiled or remained even after risk analysis, risk mitigation and successful conformity assessment. Furthermore, the study aims at providing additional data, as required by regulatory authorities.

3. Investigational Device

CIP chapter 4.7. Definition of the investigational Devices

4.7.1 Ilivia ICD family

The Ilivia/Intica/Inlexa ICD family includes the following devices:

- Ilivia 7 VR-T, VR-T DX, DR-T and HF-T QP
- Intica 7 VR-T, VR-T DX, DR-T and HF-T QP
- Intica 5 VR-T, VR-T DX, DR-T
- Inlexa 7 VR-T, VR-T DX, DR-T and HF-T QP

4.7.7 Plexa ICD lead

4. Design

CIP chapter 8. Design of the Clinical Investigation

The study is designed as a multicenter, international, non-randomized, open-label and prospective study including two subgroups: **group A** with the Ilivia ICD family and **group B** with the Plexa right ventricular ICD lead. Patients can be enrolled into both groups, if they receive both study devices, see below for more details.

Group A Ilivia ICD family

Enrollment:

In group A, a total of 105 patients will be enrolled. With an expected drop-out rate of 10% a minimum number of 94 patients will be included in the analysis set. In total, 26 patients should receive a single chamber ICD, 26 patients a dual chamber ICD and 53 patients a triple chamber ICD (CRT-D).

Group B Plexa ICD lead

Enrollment:

In group B, a total number of 185 patients will be enrolled. With an expected drop-out rate of 10% a minimum number of 166 patients will be included in the analysis set.

Tab. 4: Required visit windows (1 month is defined as 30 days)

	Window	Days post-implant
Pre-hospital discharge or wound check	+ 10 days	0 to 10
3 months post-implant	± 30 days	61 to 121
6 months post-implant	± 30 days	151 to 211

[figure not shown]

Fig. 4: Follow-up scheme of **group A** (Ilivia ICD family) and **group B** (Plexa ICD lead)

Fig. 5: Overlap of both study groups. Patients implanted with an ICD device of the Ilivia family and a Plexa ICD lead can belong to both groups A and B

5. General Statistical Procedures

5.1. Descriptive analyses

CIP chapter 11.1 Statistical design, methods and analytical procedures

For continuous variables descriptive statistics (mean, standard deviation, minimum, 1. quartile, median, 3. quartile and maximum) will be calculated. For nominal variables absolute numbers and relative frequencies based on the non-missing data will be determined. Ordinal data are described by the 1. quartile, median, and 3. quartile as well as the absolute numbers and relative frequencies based on the non-missing data of each category

Ordinal data are described by the absolute numbers and relative frequencies based on the non-missing data of each category and by the 1. quartile, median and 3. quartile, when appropriate.

For illustration, see the following standard tables based on dummy data.

Nominal - dichotomous

Variable label	Category	Missing data	Non-missing data	Absolute frequency	Relative frequency [%]
Sex	Female	1	9	5	55.6
History of AF	Yes	2	8	4	50.0

Nominal – more than two categories

NYHA class, all patients	Absolute frequency	Relative frequency [%]
NYHA I	5	62.5
NYHA II	1	12.5
NYHA III	1	12.5
NYHA IV	1	12.5
Sum	8	100.0

NYHA class, all patients; N total =10; N missing = 2

Scale / metric

Variable	N non-missing	N missing	Mean	SD	Min	Lower quartile	Median	Upper quartile	Max
Age [years]	7	3	51.7	15.0	25.0	40.0	57.0	60.0	70.0
Height [cm]	8	2	177.3	14.4	150.0	170.0	179.0	187.5	195.0
Weight [kg]	7	3	77.1	14.5	55.0	69.0	77.0	90.0	99.0

Ordinal

Variable	N non-missing	N missing	Min	Lower quartile	Median	Upper quartile	Max
NYHA class	8	2	1.0	1.0	1.0	2.5	4.0
Patient self assessment	8	2	1.0	1.0	1.0	2.0	3.0

5.2. Inferential analyses

CIP chapter 11.1 Statistical design, method and analytical procedures

For both primary hypotheses exact binomial tests are carried out. All endpoints are analysed per-protocol (PP), whereby the analysis sets are defined for each hypothesis separately.

5.3. Significance level

CIP chapter 11.3 Level of significance and the power of the study

The 2-sided level of significance is $\alpha = 2.5\%$ for each alternative hypothesis (1-sided 1.25% significance level). Thus, the 2-sided significance level of the global hypothesis of 5% (1-sided 2.5% significance level) is maintained

5.4. Missing Data

CIP chapter 11.11 Handling of missing, unused and spurious data

Missing or spurious data will not be imputed.

Spurious data, which were not clarified by the query process before CDMS closure, are indicated. If appropriate, descriptive and inferential analyses are performed both with and without such data.

5.5. Exclusion of data from confirmatory data analysis

CIP chapter 11.12 Exclusion of data from the confirmatory data analysis

If the patient has atrial fibrillation during the device based measurements, the P-wave amplitude and the atrial threshold are not included in the analysis. Protocol deviations in regard to the follow-up schedule will not result in an exclusion of data in the analysis but will be subject to query management.

If the patient has atrial fibrillation during the device based measurements, data are classified as „not measurable: no p-wave visible“ in the CRFs.

5.6. Subgroups

CIP chapter 11.9 Specification of subgroups

Results of the Ilvia ICD family and the Plexa ICD lead are analysed separately. No further subgroup analysis is planned.

5.7. Interim analyses

CIP chapter 11.6 Provision of an Interim analysis

In the BIO|MASTER.Ilivia Family / Plexa study no interim analysis is planned to accept the primary alternative hypothesis, e.g. like in a group-sequential design. However, in case of a significant discrepancy of the enrollment periods between both groups, the first group may be analyzed prior to the overall final analysis. This kind of preliminary analysis would not bias the analysis of the other group, as the hypotheses of both groups are analyzed independently. The preliminary analysis of one group (after completion of data collection for this group) would not constitute a multiple interim testing and therefore does not necessitate further statistical adjustment.

Additionally, specific data will be provided to the Australian competent authorities based on a database-freeze planned Q4 2016. This kind of preliminary analysis would not bias the further data because no investigator except the Coordination Investigator will be informed about the results. Except for safety reasons, no instruction for the further conductance of the clinical investigations will be made based on the preliminary analysis.

During the course of the study, some data may be entered in the CDMS with the signature of the investigator missing. Such data are excluded from the analysis. The following tables define which record status values are considered confirmed or not confirmed.

Variable name	Nominal vales	Variable name	Nominal vales
record_status_text	Record complete Record contains errors Open query Answered query	record_status	1 3 1149 1150

Datasets not confirmed by the investigator

Variable name	Nominal vales	Variable name	Nominal vales
record_status_text	Investigator signed Monitor approved Record Clean Field Monitor approved	record_status	1047 1051 1052 1082

Datasets confirmed by the investigator¹

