11.6 Provision for an interim analysis

In the BIO|MASTER.Ilivia Family / Plexa study no interim analysis is planned to accept the primary alternative hypothesis, e.g. like in a group-sequential design.

However, in case of a significant discrepancy of the enrollment periods between both groups, the first group may be analyzed prior to the overall final analysis.

This kind of preliminary analysis would not bias the analysis of the other group, as the hypotheses of both groups are analyzed independently. The preliminary analysis of one group (after completion of data collection for this group) would not constitute a multiple interim testing and therefore does not necessitate further statistical adjustment.

Additionally, specific data¹ will be provided to the Australian competent authorities based on a database-freeze planned Q2/Q3 2017. This kind of preliminary analysis would not bias the further data because no investigator except the Coordination Investigator will be informed about the results. Except for safety reasons, no instruction for the further conductance of the clinical investigations will be made based on the preliminary analysis.

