16.2. Variables

CIP chapter 8.3.1.1 Group A: Ilivia family related SADE-free rate through 3 months

The parameter of interest " $Ilivia_{SADE\ free}$ " is the device related SADE-d free rate per patient, which will be calculated by $Ilivia_{SADE\ free} = [1 - \text{number of patients with one or more ICD related SADEs (SADE-d}_{Ilivia}) \text{ until 3-month follow-up} \div \text{all patients in the analysis set}] * 100\%$. SADEs will be adjudicated by an internal adjudication board, whereby the seriousness and device relatedness will be re-examined. If any amply documented external physical influence (e.g. accident, sport, twiddling) or medical AE caused the SADE, it does not contribute to this endpoint. SADEs that occur later than the 3-months follow-up do not contribute to this endpoint.

In patients without 3 month FU, and in patients with a date of the 3-month Follow-Up outside the required visit window from 61 to 121 days post-implant, all SADEs until and including 121 days after implantation can contribute to the endpoint (if they fulfil the requirements for an endpoint).

Data file, list of AE evaluations, identifier parent_record_ID	Descriptive	Variable name	Variable label	Variable level	Nominal values
ae_evaluation_form_1	No	endpoint_ilivia → endpoint_ilivia1	relevant for the primary endpoint (Ilivia family related SADE-free rate)	nominal	Yes / No
ae_evaluation_form_1	No	AESTDT	Onset date	date	n.a.
ae_evaluation_form_2	No	endpoint_ilivia → endpoint_ilivia2	relevant for the primary endpoint (Ilivia family related SADE-free rate)	nominal	Yes / No
ae_evaluation_form_2	No	AESTDT	Onset date	date	n.a.

There are two evaluation CRFs. An AE is defined as endpoint relevant when both evaluations came to this result. All divergent evaluations have to be reported⁷⁰.

Data file, identifier patient_display_id_full	Descriptive	Variable name	Variable label	Variable level	Nominal values
implantation_general_data	No	imp_visdate	Date of implantation	date	n.a.
data_SAR	No	enddate_Ilivia_SAR	Date of Ilivia study termination	date	n.a.
data_SAR	No	date_1stIliviaSADE_SAR ⁷¹	Date of 1 st primary Ilivia-related SADE	dummy	No
data_SAR	No	Ilivia_primEP_analysis_set_SAR ⁷²	Analysis set Ilivia primary endpoint	nominal	Yes /No
data_SAR	Yes	Ilivia_primEP_SAR ⁷³	Ilivia-related SADE(s)	nominal	Yes /No

⁷⁰ Report any endpoint_ilivia1 ≠ endpoint_ilivia2

⁷¹ date_1stIliviaSADE_SAR = minimum AESTDT with
endpoint_ilivia1 = Yes AND
endpoint_ilivia2 = Yes
per patient_display_id_full

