⁷² IF analysis_set_Ilivia_SAR = Yes AND
date_1stIliviaSADE_SAR - imp_visdate ≤ 60days OR enddate_Ilivia_SAR - imp_visdate ≥ 61 days
THEN Ilivia_primEP_analysis_set_SAR = Yes
ELSE Ilivia_primEP_analysis_set_SAR = No

⁷³ IF analysis_set_Ilivia_SAR = Yes AND
date_1stIliviaSADE_SAR ≠ missing AND
{[fu3_visdate ≠ missing AND fu3_visdate is compliant AND date_1st_IliviaSADE_SAR ≤ fu3_visdate] OR
[fu3_visdate ≠ missing AND fu3_visdate is not compliant
AND date_1st_IliviaSADE_SAR - imp_visdate ≤ 121 days] OR
[fu3_visdate = missing AND date_1stIliviaSADE_SAR - imp_visdate ≤ 121days] }
THEN Ilivia_primEP_SAR = Yes
ELSE Ilivia_primEP_SAR = No

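### Preliminary analyses leave out records the investigator has not confirmed, with no exemption for safety forms, so an early SADE-free rate may omit reported SADEs and be biased in either direction

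*SAP*

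**What the plan says.** SAP 5.7 (Interim analyses) describes two occasions on which data are analysed before the end of the study. The first is a data cut for a regulator: "specific data will be provided to the Australian competent authorities based on a database-freeze planned Q4 2016". The second is early analysis of whichever group completes first. Protocol 11.6 says of it that "the first group may be analyzed prior to the overall final analysis", and SAP 5.7 adds: "The preliminary analysis of one group (after completion of data collection for this group) would not constitute a multiple interim testing".

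The same section then sets the data rule: "some data may be entered in the CDMS with the signature of the investigator missing. Such data are excluded from the analysis". Its first status table lists what is not confirmed: "Record complete Record contains errors Open query Answered query". No form type is exempt.

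The primary endpoint is built from two evaluation forms per event (SAP 16.2 and 23.2): "An AE is defined as endpoint relevant when both evaluations came to this result". The event date is read from those forms as well. A patient with no qualifying event date falls to the default, "ELSE Ilivia_primEP_SAR = No", which means event-free. Membership of the primary analysis set needs either an event within 60 days of implantation or "enddate_Ilivia_SAR - imp_visdate ≥ 61 days". The Plexa code has the same structure.

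**The concern.** The rule looks like ordinary data hygiene, but it does not act neutrally on this endpoint. Dropping a measurement record loses a measurement. Dropping an event record turns a failure into a success, because absence of a record is read as absence of an event.

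SADE records are plausibly exposed to the rule. Protocol 18.9 requires entry within 24 hours of detection, Protocol 18.8.1 asks for reports even when incomplete, and Protocol 12.1 says incomplete data are queried. No deadline for the investigator's signature appears in either document.

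Evaluation forms raise a further question. An internal board adjudicates SADEs, while Protocol 12.2 lets only investigators sign entries. The SAP does not say how a board form becomes confirmed.

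At stake is a preliminary safety result, possibly a group's own primary test, that leaves out events already reported to the sponsor.

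**Working it through.** **Inputs.** Null rate 90% SADE-free (Protocol 8.3.1); one-sided level 1.25% per hypothesis (11.3); 94 evaluable and 105 enrolled in A, 166 and 185 in B, with 10% drop-out and assumed rates of 98% and 97% (11.2); termination at 4 event patients in A and 9 (or 10) in B (11.7).

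**The plan's own figures.** With X events, the test passes if P(X ≤ x | n, 0.10) ≤ 0.0125.
- A, n=94: at most 3 events, exact level 0.01246, power 0.880 at 98%. Enrolment 94/0.9 = 104.4, so 105.
- B, n=166: at most 8 events, exact level 0.01215, power 0.936 at 97%. Enrolment 166/0.9 = 184.4, so 185.

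The sample sizes and the limits of 4 and 9 reproduce.

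**One lost event.**

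| Group | All events counted | Event lost, patient stays in set | Event lost, patient leaves set |
|---|---|---|---|
| A | 4/94, p=0.0357, fail | 3/94, p=0.01246, pass | 3/93, p=0.0134, fail |
| B | 9/166, p=0.0260, fail | 8/166, p=0.01215, pass | 8/165, p=0.0129, fail |

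Which column applies depends on when the patient leaves the study. Endpoint events include complications corrected invasively (Protocol 18.11). Explantation or replacement of either device, or repositioning of Plexa, is mandatory drop-out (8.8.4.1). For Plexa replacement or repositioning, termination is dated to the revision (8.8.5). If that date is day 60 or earlier and the event record is excluded, neither condition for entering the set is met, so the patient leaves numerator and denominator together. A patient with a later event, or whose Ilivia device is only repositioned, can stay in.

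**Numerator effect.** Let f be the share of event patients whose event record is excluded while they stay in the set. The documents give no value; 5% to 30% is an assumption. The chance of passing at a true 90% is P(X ≤ 3 | 94, 0.10(1−f)) in A and P(X ≤ 8 | 166, 0.10(1−f)) in B.

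| f | Rate read at true 90% | A | B |
|---|---|---|---|
| 0 | 90.0% | 0.0125 | 0.0122 |
| 5% | 90.5% | 0.0180 | 0.0201 |
| 10% | 91.0% | 0.0258 | 0.0325 |
| 20% | 92.0% | 0.0514 | 0.0789 |
| 30% | 93.0% | 0.0981 | 0.1719 |

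At the planning rates the shift is small: for f of 10% to 30%, 98% reads 98.2% to 98.6% and 97% reads 97.3% to 97.9%.

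**Denominator effect.** Let g be the share of patients without a confirmed termination form (also an assumption), with true rate t and retained events falling by day 60. Successes are t(1−g) + (1−t)f(1−g) and failures are (1−t)(1−f). With t=95% and f=10%:
- g=0: 0.955/1.000 = 95.5%
- g=10%: 0.8595/0.9045 = 95.0%
- g=30%: 0.6685/0.7135 = 93.7%
- g=50%: 0.4775/0.5225 = 91.4%

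The net direction therefore depends on f and g. The footnoted code does not say how a missing event or termination date is evaluated, so the size of this effect also depends on programming.

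**The case against.** Restricting a preliminary cut to investigator-confirmed data is a normal integrity rule, and the SAP notes that data can still change before database closure. Several further objections carry weight.

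- **Authority data.** A reader might infer that a SADE-free rate goes to the Australian authority. The documents say only that specific data will be provided. Protocol 11.6 defers the variable list to the SAP, and SAP 5.7 gives none. Reporting of SAEs and SADEs to authorities runs separately under Protocol 18.8.3, so the documents do not show that events would be hidden from the regulator.
- **Evaluation forms.** Their coverage by the rule is inferred. An investigator-signature filter does not obviously fit forms completed by an internal board, and a literal reading could remove every event, which is hardly intended. This stands as a reason to say what applies; it does not supply an exemption.
- **Direction.** A reader might conclude that the rate is necessarily biased upward. Missing termination forms pull the other way. With first enrolment expected in June 2016 and regular termination at six months, few event-free patients could have a termination date at a Q4 2016 freeze.
- **First-completed group.** It is analysed only after its data collection is complete. Qualifying events fall by day 121 at the latest, while regular follow-up runs to days 151–211, which leaves time for query resolution and signature. Protocol 11.7 also stops group A on confirmed knowledge of four event patients, so the sponsor would know of a fourth. The risk here is smaller, though nothing requires every record to be signed before the analysis.

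**Conclusion.** The point holds as a gap in the rule for preliminary analyses. SAP 5.7 excludes unconfirmed records without exempting safety forms, and the endpoint code reads a missing event as success. A preliminary safety result may therefore omit reported SADEs, and the SADE-free rate may be biased in either direction.

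The pass/fail change from one lost event is real at the margin in both groups, but only when the patient remains in the set through a termination date at day 61 or later. The inflated chances of passing rest on the same condition and on assumed loss shares. They illustrate sensitivity and do not estimate what will happen. The documents do not support saying that a biased rate will be submitted to an authority, or that a primary hypothesis will be accepted wrongly.

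**What to change.** Amend SAP 5.7 so that, in any preliminary safety analysis:
- all reported AE, SADE, device-deficiency and endpoint-evaluation records count whatever their status, with unconfirmed ones flagged by form;
- the enrolment, implantation and termination records that define the denominator follow the same status rule, so that both parts of the rate rest on the same footing;
- the confirmed-only result is shown as a sensitivity analysis;
- board evaluation forms are stated not to need an investigator signature.

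Keep the exclusion for measurement data. The section should also list the variables for the authority, and its freeze date (Q4 2016) should be reconciled with the one in Protocol 11.6 (Q2/Q3 2017), since the date affects how many records would be unconfirmed.

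The cost is a few SAP sentences and no new data. The downside is that a preliminary result may include events later reclassified and may look slightly less favourable.
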